9.3.9 MEASURES OF CRAVING (VAS)

Measures of craving include Desire to Use VAS and Need to Use VAS, will be administered using unipolar 100 mm VAS (“In the past week/month, how intense has been your average desire/need to use “drug name?”, where 0 = No desire to use and 100 mm= Strongest possible desire, and from 0=No need to use and 100 mm=Strongest possible need, respectively). They will be measured at baseline and some selected post baseline visits (For more detail, please refer to Table 3, Schedule of Assessments, in Section 10 of the protocol, TRIAL PROCEDURES AND ASSESSMENTS).

Changes from baseline in the above VASs will be derived by subtracting the baseline values from the post-baseline values, thus, negative changes are indicative of improvement. Changes from baseline in measurements of craving will be analyzed via Analysis of Covariance (ANCOVA) model with treatment and baseline effects. Treatment effects and treatment differences will be estimated. The two-sided 95% confidence intervals the treatment differences will be presented. In this primary analysis, missing values will be imputed using Last Observation Carried Forward (LOCF) method.

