5.2. Trial Rationale

Opioid drug use disorder is a major health and social issue and is a chronic medical condition that often requires long-term maintenance treatment. An important aim of the treatment programs for opioid drug dependence is to assist in helping the patients stop abusing illicit drugs. Further important aims are to improve their mental and physical health, as well as their social conditions. This can be achieved by increasing patients' quality of life and will also reduce the burden on the society and relatives. Moreover, opioid addicts often inject with used syringes and

needles, and thus expose themselves to high risk of transmission of infectious diseases, including human immune deficiency virus (HIV) and hepatitis C.

Opioid maintenance treatment, such as SL BPN, is one of the most effective treatment options available for opioid dependent drug users and is associated with substantial reductions in illicit opioid use, criminal activity, deaths, and HIV transmission (6). Patients often discontinue treatment prematurely, an outcome associated with higher rates of relapse to drug use, which means that treatment strategies that aim to keep patients in treatment longer and/or improve patient adherence may have additional advantages (7). While daily dosing with SL BPN has proven effective, the need for daily administration of treatment may negatively influence patients' adherence and duration of therapy. Moreover, SL tablets or film can be easily abused and diverted for illicit use, injected for greater effect, or accidentally ingested, especially by children (7, 8). The limitations associated with SL BPN are of particular relevance to patients who have children at home, to those who have difficulty making frequent visits to the physician's office (e.g., patients in remote locations, those with limited mobility, or those who travel frequently) or to those who have difficulty managing the responsibility of daily dosing.

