7.1.3. Phase 2 (Monthly Visits)

Weeks 13 to 24:

At Week 13 visit, all subjects will be transitioned to monthly treatment (dispensing for SL BPN/Placebo or SC injections). Before transitioning to CAM2038 q4w, subjects will be evaluated for the stability criteria described above.

Treatment: Subjects will receive the following treatments for a duration of 12 weeks:

- Group 1 (SL BPN): daily SL BPN + injections of once monthly SC placebo
- Group 2 (CAM2038): injections of once monthly CAM2038 q4w SC + daily SL placebo

Subjects will therefore receive their first dose of CAM2038 q4w (or placebo) at the beginning of Week 13 (± 2 days), preferably Monday. Subjects will receive their monthly SL tablets (SL BPN or placebo) and an SC injection (CAM2038 q4w or placebo) while on site.

Subjects will continue to receive the daily dose of SL BPN or SL placebo that they received at the end of Phase 1. Based on their CAM2038 q1w (or SC placebo) dose at the end of Phase 1, subjects will be transitioned to the following doses of CAM2038 q4w or placebo SC injection in Phase 2:

- 16 mg CAM2038 q1w/placebo = 64 mg CAM2038 q4w/placebo
- 24 mg CAM2038 q1w/placebo = 96 mg CAM2038 q4w/placebo
- 32 mg CAM2038 q1w/placebo = 128 mg CAM2038 q4w/placebo

Dosage adjustment will be allowed during Phase 2 at the monthly scheduled visits only, up to a maximum of 32 mg SL BPN (or placebo) and up to 160 mg CAM2038 q4w (or placebo), as outlined in Section 9.1.2.

Subjects will return to the clinic for monthly trial visits during Phase 2. In addition to the monthly visits, subjects will return to the clinic to provide 3 random urine toxicology samples during Phase 2 of the trial. At each scheduled monthly visit, SL tablets (BPN or placebo) sufficient to last until the next visit will be dispensed. Subjects will also receive SC injections on site at the Week 13 (± 2 days), 17 and 21 visits (± 7 days). Urine toxicology samples will be taken at each scheduled or random visit for illicit testing of opiates/opioids and self-reports of illicit drug use will be collected in connection to the urine samplings. Other drugs of abuse will also be assessed. During Phase 2, a total of 6 urine toxicology samples will be collected; 3 at scheduled visits (1 per month) and 3 at random urine toxicology visits. COWS/SOWS and VAS will be performed at each scheduled trial visit. Other outcome measures and safety assessments are outlined in Table 4.

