All efforts will be made to ensure that all subjects are briefed on the importance of the clinical trial and collection of data they provide. Emphasis should be made to subjects that it is more important to attend all visits and be truthful about their use of illicit opioids than to be “clean”. The subjects will be told that they will not be punished or discontinued from the trial for using illicit opioids and their truthful information on illicit opioid use will be an important component of the trial data collection. All efforts should be made by the Investigator to continue collection of urine samples at the protocol-defined trial visit intervals, concomitant medications, and AEs in subjects that discontinue trial drugs, unless the subject withdraws his/her consent at the time of early discontinuation. The Investigator should also ask the subject to return for the Follow-up assessments for Week 25 (EOT), provided that the subject has not withdrawn consent for those assessments. If a subject refuses to complete early termination procedures and/or Follow-up, this information will be recorded.

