ⁱ It is the Investigator’s responsibility to understand and comply with all laws and regulations that apply to HIV, Hepatitis B, and Hepatitis C and testing of blood. Hepatitis B/C and HIV testing is required unless a site’s IRB prohibits such testing.

Trial Period/Phase:	Screening	Phase 1 (Weekly Visits)							
	Month:	-1	M1				M1-3		
	Week:	-3 to -1	W1				W2-W11		W12
	Day:	-21 to -1	D1 ^a	D2	D3	D4	D5-7	D8	Weekly ^b
Dispense Treatment Identification Card		X							
Urine Toxicology	X	X					X	Weekly	X
Illicit Drug Use Self-Report	X	X					X	Weekly	X
SOWS, COWS, VAS ^j	X	X	X		X	(X)	X	Weekly	X
C-SSRS ^k	X	X	X		X	(X)	X	Weekly	X
Measurement of Morning Desire to Use/Need to Use							X	Weekly	X
SL BPN or SL placebo dispensing		X	X		X	(X)	X	Weekly	X
SL BPN or SL placebo administration ^l		X	X	X	X	Daily	X	Daily	X
CAM2038 q1w or placebo SC injection ^m		X			X	(X)	X	Weekly	X
Psychosocial Counseling		X					X	Weekly	X
Adverse Events ⁿ	X	X	X		X	(X)	X	Weekly	X
Concomitant Medications/Procedures	X	X	X		X	(X)	X	Weekly	X
On-site visits	X	X	X		X	(X)	X	Weekly	X

Abbreviations: BMI=body mass index; BPN=buprenorphine; COWS=Clinical Opiate Withdrawal Scale; C-SSRS=Columbia Suicide Severity Rating Scale; D=day; DSM-V= Diagnostic and Statistical Manual of Mental Disorders – Fifth Edition; ECG=electrocardiogram; HIV=human immunodeficiency virus; M=month; SC=subcutaneous; SL=sublingual; SOWS=Subjective Opiate Withdrawal Scale; VAS=visual analogue scale; W=week (X) indicates as needed based on the individual subject.

^j SOWS/COWS/VAS will be completed each time the subject visits the clinic, as needed based on titration and dosage adjustment. On Day 1, COWS, SOWS and VAS will be completed before the test dose is administered (baseline). COWS will also be completed after the test dose on Day 1 to evaluate tolerability, and on Day 2.

^k Screening version at Visit 1 (Screening), Since Last Visit version at all subsequent visits.

^l Not to exceed 24 mg SL BPN (or placebo) per day, this administration will be done at home.

^m Not to exceed 32 mg CAM2038 q1w (or placebo) per week.

ⁿ Any spontaneously reported adverse event will be recorded after the subject signs the informed consent form. In addition, adverse events will be elicited using a non-leading question each time the subject visits the clinic.

Table 4 Schedule of Assessments: Phase 2 (Monthly Visits) and Follow-up

Trial Period/Phase:	Phase 2 (Monthly Visits)						Follow-up			
	Month:	M4		M5		M6		M7		

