9.3 EXPLORATORY EFFICACY VARIABLES

Exploratory efficacy variables will include:

- Primary endpoint RR for Phase 1;
- Primary endpoint RR for Phase 2;
- Percentage negative urine samples in Phase 1;
- Percentage negative urine samples in Phase 2;
- Percent of subjects with evidence of no illicit opioid use by time point;
- Cumulative percentage of subjects with evidence of no illicit opioid use after two months of treatment by time point (from Week 9 to Week 25);
- Percent of subjects with no self-reported illicit opioid use by time point;
- Percent of subjects meeting criteria of stability at Week 13;
- Measures of craving: Desire to Use visual analog scale (VAS) and Need to Use VAS;
- Measures of withdrawal: Clinical Opiate Withdrawal Scale (COWS) and Subjective Opiate Withdrawal Scale (SOWS);
- Percent of subjects without evidence of using other drugs of abuse by time point;
- Supplemental BPN use;
- Additional supplemental counseling;
- Measures of morning need to use/desire to use

9.3.1 RESPONSE RATE (RR) FOR PHASE 1

The treatment differences in RR based on the primary responder definition and based on responder for Phase 1 will be analyzed using chi square test. The percentages for each treatment and between treatment percentage differences will be estimated. The 95% confidence intervals of the estimates will be presented using normal approximation.

9.3.2 RESPONSE RATE (RR) FOR PHASE 2

The treatment differences in RR based on the primary responder definition for Phase 2 will be analyzed using chi square test. The percentages for each treatment and between treatment percentage differences will be estimated. The 95% confidence intervals of the estimates will be presented using normal approximation.

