9.3.10 MEASURES OF WITHDRAWAL SYMPTOMS

Measures of withdrawal include COWS and SOWS. The COWS is comprised of 11 items each with a score of 0 through 4. Higher scores are associated with greater withdrawal symptoms. The items are meant to be objective (e.g., resting pulse rate) measures of patient’s withdrawal symptoms. The SOWS is comprised of 16 items each with a score of 0 through 4. Higher scores are associated with greater withdrawal symptoms. The items are statements which are evaluated by the patient and are there for subjective (e.g., I feel anxious, 0 = not at all, 1 = a little, 2 = moderately, 3 = quite a bit, 4 = extremely). Both COWS and SOWS will be measured at baseline and some selected post baseline visits (For more detail, please refer to Table 3, Schedule of Assessments, in Section 10 of the protocol, TRIAL PROCEDURES AND ASSESSMENTS).

If there are ≥ 3 (i.e., $\geq 20\%$) missing items in the COWS scale at a given visit or ≥ 4 (i.e., $>20\%$) missing items in the SOWS scale at a given visit, the COWS/SOWS score for that visit will be missing. If there are 1 or 2 missing items for the COWS assessment then the total of the non-missing items will be calculated and the product of the calculated total and $11/(11 - \# \text{ missing})$ will be used for the COWS score for that visit. If 3 or fewer items are missing for the SOWS score then the total of the non-missing items will be calculated and the product of the calculated total and $16/(16 - \# \text{ missing})$ will be used for the SOWS score. Missing total scores or scores with more than two missing components in COWS, or more than 3 missing components in SOWS, will be imputed using LOCF method.

Changes from baseline in COWS and SOWS will be derived by subtracting the baseline values from the post-baseline values, thus, negative changes are indicative of improvement. Changes from baseline in measurements of withdrawal will be analyzed via ANCOVA model with treatment and baseline effects. Treatment effects and treatment differences will be estimated. The two-sided 95% confidence intervals

of the treatment differences will be presented. In this primary analysis, missing values will be imputed using LOCF method.

9.3.11 PERCENT OF SUBJECTS WITHOUT EVIDENCE OF USING OTHER DRUGS OF ABUSE BY TIME POINT

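### The exploratory craving and withdrawal scores are analysed only by ANCOVA with LOCF, which can create or mask a difference if dropout is unequal while scores are still falling

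*SAP*

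**What the plan says.** SAP 9.3.9 specifies the model for the craving scales: "Changes from baseline in measurements of craving will be analyzed via Analysis of Covariance (ANCOVA) model with treatment and baseline effects". It then adds: "In this primary analysis, missing values will be imputed using Last Observation Carried Forward (LOCF) method". SAP 9.3.10 uses the same model for COWS and SOWS: "In this primary analysis, missing values will be imputed using LOCF method". SAP 9.3.14 repeats the LOCF sentence for the morning desire and need scores.

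Status: SAP 9.3 lists "Measures of craving: Desire to Use visual analog scale (VAS) and Need to Use VAS" and the withdrawal scales among the exploratory variables. None of them is in the five ordered hypotheses of SAP 9.5. The word primary in 9.3.9 and 9.3.10 therefore means the main analysis of an exploratory variable.

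Collection: the scores are repeated measures. For Phase 1, Table 3 of Protocol section 10 notes that "SOWS/COWS/VAS will be completed each time the subject visits the clinic, as needed based on titration and dosage adjustment". For Phase 2, Protocol 7.1.3 states that "COWS/SOWS and VAS will be performed at each scheduled trial visit". After trial drug is stopped, Protocol 8.3 asks sites to "continue collection of urine samples at the protocol-defined trial visit intervals, concomitant medications, and AEs in subjects that discontinue trial drugs". Craving and withdrawal scores are not in that list, although subjects are also asked to return for the Week 25 assessments.

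Sensitivity: Protocol 12.3.2.3 promises sensitivity analyses under several imputation methods, to be described in the SAP. For these scores the SAP describes none. It does not justify LOCF, and it does not say whether a baseline value is carried forward when a subject has no later score.

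**The concern.** Subjects start treatment in at least mild withdrawal (Protocol 7.1.2), and scores should then fall. LOCF holds a subject who leaves early at the last, higher value and compares it with later values of subjects who stayed. The arm that loses more subjects early then looks worse, even if symptoms run the same course in both arms.

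The documents make dropout likely and unequal dropout possible. Protocol 5.2 says "Patients often discontinue treatment prematurely" and argues that the depot may improve adherence. SAP 9.5 tests retention for non-inferiority with a 15-point margin and then for superiority. If CAM2038 retains more subjects, LOCF could show a craving benefit that comes from retention alone. If it retains fewer, LOCF could hide a real benefit. Protocol 10.5 relies on COWS and SOWS to show that withdrawal is controlled as well as on SL BPN, so these estimates will be read even though they are exploratory.

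**Working it through.** **The plan's own figure.** The documents give no power, SD, trajectory or dropout rate for these scores. The only power stated in the SAP is for the primary endpoint (SAP 9.6: 190 per arm, 70% response in both arms, 13.5-point margin). It reproduces: SE = √(2 × 0.7 × 0.3 / 190) = 0.0470; Φ(0.135/0.0470 − 1.96) = 0.819, against the stated 82%. Nothing in it depends on how the craving or withdrawal scores are analysed.

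**Assumed inputs (not in the documents).** Mean VAS m(t) = 15 + 55·exp(−t/τ) mm, with t in weeks from Day 1, the same in both arms. Time constant τ is 1 week (early plateau), 4 weeks, or 8 weeks (slow decline). Retention R at Week 25 is 60% in the control arm and 5, 10 or 15 points lower in the test arm. The largest gap matches the retention margin in SAP 9.5.

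**Closed form.** Post-baseline visits are Weeks 2 to 13, 17, 21 and 25, that is t = 1 to 12, 16, 20 and 24. All subjects are seen at t = 1, and dropout is then at a constant rate unrelated to score: S(t) = R^((t−1)/23). The LOCF mean at Week 25 is

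Σ m(tⱼ)·[S(tⱼ) − S(tⱼ₊₁)] over the first 14 visits, plus m(24)·S(24).

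Example, τ = 4: R = 0.60 gives 19.10 mm and R = 0.50 gives 20.36 mm, a false difference of 1.26 mm. The true mean is 15 + 55·exp(−6) = 15.1 mm in both arms.

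| τ | Gap 5 points | Gap 10 points | Gap 15 points |
|---|---|---|---|
| 1 week | 0.12 mm | 0.24 mm | 0.38 mm |
| 4 weeks | 0.61 mm | 1.26 mm | 1.95 mm |
| 8 weeks | 0.97 mm | 1.99 mm | 3.07 mm |

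With equal dropout the false difference is zero.

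**Simulation.** 600 runs per row, 190 per arm, seven post-baseline visits, SD about 23 mm, no true effect, nominal retention 60% against 45%. Realised retention was 63–64% against 50–51% where dropout depended on score. The mixed model has unstructured covariance, with treatment and baseline by visit.

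| Course and dropout | LOCF: bias, rejection | Mixed model: bias, rejection |
|---|---|---|
| Slow, unrelated to score | 3.81 mm, 32.0% | −0.09 mm, 3.5% |
| Slow, depends on last observed score | 3.78 mm, 31.3% | 0.07 mm, 4.8% |
| Slow, depends on unobserved score | 3.53 mm, 29.0% | −0.68 mm, 5.5% |
| Plateau, unrelated to score | 0.88 mm, 6.8% | −0.05 mm, 6.0% |
| Plateau, depends on last observed score | 1.42 mm, 8.5% | 0.06 mm, 5.2% |
| Plateau, depends on unobserved score | 0.88 mm, 7.0% | −0.86 mm, 6.2% |

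Simulation error on a 5% rejection rate is √(0.05 × 0.95/600), about 0.9 points. Seven visits lie further apart than the trial's fifteen, so older values are carried forward and the LOCF bias is somewhat larger than in the closed form. With a nominal 10-point gap and slow decline, LOCF gives 2.33 to 2.71 mm with rejection near 18% under the first two dropout mechanisms.

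**Masking.** With a true effect of −8 mm, slow decline, a 15-point gap and dropout unrelated to score, LOCF estimates −4.1 mm and the mixed model −7.9 mm.

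**Size of the covariance matrix.** Fifteen post-baseline visits, leaving aside the extra Week 1 scores and Week 29, give 15 × 16/2 = 120 parameters.

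**The case against.** The strongest reply is that little hangs on this. The endpoints are exploratory, and dropout is reported openly through disposition (SAP 7.1) and the retention difference with its interval (SAP 9.2.3). The larger biases need a slow decline and a wide gap, both assumed. With a faster course falling from 60 to 20 mm (τ = 4), dropout of 30% against 40% spread evenly over time, and the same SD, simulation gives a false difference of only 1.0 mm and 7.4% rejection. That is below one unadjusted standard error, 23 × √(2/190) = 2.4 mm. This stands, and it limits the weight of the point.

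A reader might infer more than the documents support, in three ways.

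- That any dropout difference gives a misleading result. Protocol 5.2 reports that, in an earlier trial, most patients stayed below the mild threshold on COWS and SOWS up to and beyond 7 days after one dose. That suggests an early plateau and little bias for those scales. For craving, the same section puts stabilisation at 1 to 2 months, so a slower fall is plausible.
- That LOCF makes the standard error too small. An ANCOVA at one visit uses one value per subject. With 40% dropout in both arms, simulation gave a model SE of 2.17 against an empirical SD of 2.15, and 4.7% type I error. The problem is bias under unequal dropout.
- That a mixed model is better without qualification. It is unbiased under missing at random. Protocol 5.2 links early discontinuation to relapse, which makes that assumption doubtful. With an early plateau and dropout that depends on the unobserved score, its bias is as large as that of LOCF. With equal dropout, unrelated to score, and a true −8 mm effect, both are unbiased, but LOCF rejects in 91–98% of runs and the mixed model in 86–87%.

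**Conclusion.** The point holds as a modest improvement to the analysis of exploratory endpoints. LOCF ANCOVA is the only analysis written for the craving and withdrawal scores, and the promised sensitivity analyses are not written for them. If dropout is unequal while scores are falling, the estimate mixes symptom level with time of dropout and can err in either direction.

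On a 100 mm VAS, under the assumptions above, the false difference is about 0.1 to 1.4 mm with an early plateau and about 2 to 4 mm with a slow decline and a gap of 10 to 15 points. These figures do not convert to COWS or SOWS points. They measure error against the scores that subjects would have had if all had stayed; the SAP does not say whether that is the quantity it wants. Nothing here affects the primary analysis, the sample size or alpha.

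**What to change.** In SAP 9.3.9 and 9.3.10, make a mixed model for repeated measures on observed scores the main analysis: treatment, visit, treatment by visit, baseline and baseline by visit, with the treatment contrast and 95% interval at each visit.

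- Covariance: unstructured first, then a prespecified order of fallbacks, for example heterogeneous Toeplitz and then a simpler structure with robust standard errors.
- Item-level rules: the proration of COWS and SOWS for a few missing items can stay. The sentence that fills a missing total by LOCF should go.
- State whether scores recorded after trial drug is stopped, such as at Week 25, enter the model, and how subjects with no post-baseline score are handled.
- Keep LOCF at most as a sensitivity analysis.
- Add one missing-not-at-random analysis, for example multiple imputation with the imputed scores of dropouts shifted upward over a stated range. This also delivers what Protocol 12.3.2.3 promised.
- Remove LOCF from SAP 9.3.14 in the same way. Protocol 10.3.7 starts the morning scores on Day 8, so they have no pre-treatment baseline, although 9.3.14 assumes one. The SAP must say what replaces the baseline terms.

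Cost: SAP wording and standard code, with no new subjects, visits or data. Intervals may be somewhat wider, the main model relies on missing at random, and the covariance fallback has to be fixed before unblinding.

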9.3.10 MEASURES OF WITHDRAWAL SYMPTOMS

Measures of withdrawal include COWS and SOWS. The COWS is comprised of 11 items each with a score of 0 through 4. Higher scores are associated with greater withdrawal symptoms. The items are meant to be objective (e.g., resting pulse rate) measures of patient’s withdrawal symptoms. The SOWS is comprised of 16 items each with a score of 0 through 4. Higher scores are associated with greater withdrawal symptoms. The items are statements which are evaluated by the patient and are there for subjective (e.g., I feel anxious, 0 = not at all, 1 = a little, 2 = moderately, 3 = quite a bit, 4 = extremely). Both COWS and SOWS will be measured at baseline and some selected post baseline visits (For more detail, please refer to Table 3, Schedule of Assessments, in Section 10 of the protocol, TRIAL PROCEDURES AND ASSESSMENTS).

If there are ≥ 3 (i.e., $\geq 20\%$) missing items in the COWS scale at a given visit or ≥ 4 (i.e., $>20\%$) missing items in the SOWS scale at a given visit, the COWS/SOWS score for that visit will be missing. If there are 1 or 2 missing items for the COWS assessment then the total of the non-missing items will be calculated and the product of the calculated total and $11/(11 - \# \text{ missing})$ will be used for the COWS score for that visit. If 3 or fewer items are missing for the SOWS score then the total of the non-missing items will be calculated and the product of the calculated total and $16/(16 - \# \text{ missing})$ will be used for the SOWS score. Missing total scores or scores with more than two missing components in COWS, or more than 3 missing components in SOWS, will be imputed using LOCF method.

Changes from baseline in COWS and SOWS will be derived by subtracting the baseline values from the post-baseline values, thus, negative changes are indicative of improvement. Changes from baseline in measurements of withdrawal will be analyzed via ANCOVA model with treatment and baseline effects. Treatment effects and treatment differences will be estimated. The two-sided 95% confidence intervals

of the treatment differences will be presented. In this primary analysis, missing values will be imputed using LOCF method.

9.3.11 PERCENT OF SUBJECTS WITHOUT EVIDENCE OF USING OTHER DRUGS OF ABUSE BY TIME POINT

The list of drugs of abuse will include cocaine, benzodiazepines, barbiturates, amphetamines, phenycyclidine, and THC. Percent of subjects without using each of the above drugs by time point (by scheduled post baseline visit) will be analyzed using chi square tests. The percentages for each treatment and between treatment percentage differences will be estimated. The 95% confidence intervals of the estimated treatment differences will be presented.

